7.5.1.2 OS sensitivity Analyses

The following OS sensitivity analyses will be performed:

- 1) OS will be compared between treatment groups using a two-sided unstratified log-rank test.
- 2) OS will be compared between the treatment groups using the strata as determined at baseline (CRF source). This analysis will be performed only if stratification variable at IVRS and at baseline disagree for at least 10% of the randomized subjects.
- 3) OS will be compared between the treatment groups using a two-sided stratified log-rank test in All treated subject population, using arm, as randomized. This analysis will be performed only if the proportion of randomized but never treated subjects exceeds 5%.
- 4) A multivariate Cox regression model will be used to estimate the treatment effect after including the following covariates measured at baseline: Backward selection method will be used to eliminate non-significant covariates at level 0.15.
 - a) Age (continuous covariate)
 - b) Steroid Use (Yes, No)
 - c) Performance Status (Karnofsky scale) (≤ 80 , > 80)

The level of the covariate normally associated with the worst prognosis will be coded as the reference level. The hazard ratio associated with treatment and with each of the baseline covariates will be presented along with associated 95% CIs.

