7.5.1 Overall Survival

7.5.1.1 Primary Analysis

The primary objective of the study is to compare the overall survival between treatment groups in all randomized subjects.

Overall survival will be compared between the treatment groups using stratified log-rank test (5% alpha level), the two-sided log-rank p-value will be reported. The stratified hazard ratio between the treatment groups will be presented along with the 95% CI.

OS will be estimated using the KM techniques. A two-sided 95% CI for median OS in each treatment group will be computed via the log-log transformation method. OS rates at fixed time points (e.g. 12, 18, 24 months, depending on the minimum follow-up) will be presented along with their associated 95% CIs. These estimates will be derived from the Kaplan Meier estimate and corresponding CIs will be derived based on Greenwood formula for variance derivation and on log-log transformation applied on the survivor function. Minimum follow-up must be longer than the timepoint to generate the estimate. In case the minimum follow-up is less than the timepoint, but it is judged that data immaturity does not affect interpretability of the results, the estimate will be provided.

The status of subjects who are censored in the OS KM analysis will be tabulated for each treatment group using the following categories:

- On-study (on-treatment, in follow-up)
- Off-study (lost to follow-up, withdraw consent, never treated)

To examine the assumption of proportional hazards in the Cox regression model, in addition to treatment, a time-dependent variable defined by treatment by time interaction will be added into the model. A two-sided Wald Chi-Square p-values of less than 0.1 will indicate a potential nonconstant treatment effect. In that case, additional exploratory analyses may be performed.

A by-subject listing will be presented including treatment arm, OS, whether the subject was censored, and if censored, the subject’s status.

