		
Section 7.5.1.1 Primary Analysis: a by-subject listing is added.
 
Section 7.5.1.2 OS sensitivity Analyses: The covariate of prior surgery is delete from the multivariate analysis since the model is stratified by IVRS resection which would correlate with the covariate.
 
Section 7.5.3.1 Primary Analysis: Censoring categories are added; a by-subject listing is added.
 
Section 7.5.3.2 Sensitivity Analysis: Table 7.5.3.2-1 is replaced by figure 7.5.3.2-1.
 
Section 7.5.5 Relationship between OS or PFS and TMB: new analysis.
 
[REDACTED]
 
[REDACTED]
 
[REDACTED]
 
[REDACTED]
 
Section 7.6 Safety: Reference to Core Safety SAP is replaced by the appropriate text due to retirement of Core Safety SAP.
 
[REDACTED]
 
[REDACTED]
 
[REDACTED]
 
[REDACTED]
 
[REDACTED]
 
[REDACTED]
 
[REDACTED]
 
[REDACTED]
 
[REDACTED]

Table 10-1: Document History

Version Number	Author	Description
		
[REDACTED]
 
[REDACTED]
 
[REDACTED]
 
[REDACTED]
 
[REDACTED]
 
Throughout the document:
 
Multiple changes in the structure and language were made for the sake of compliance with the IO core SAP and without modification of the text meaning;
 
Multiple editorial changes.

2.0	[REDACTED]	
Revision Date: 19-Sep-2018
 
Revised SAP according to protocol amendment 09. Major changes included in this amendment are:
 
Removal of the interim analysis for superiority of the primary endpoint of OS.
 
Addition of a secondary endpoint that evaluated, in newly diagnosed, unmethylated MGMT GBM, any relationship between OS or PFS and TMB in the RT + nivolumab arm compared to the RT + TMZ control arm.

1.0	[REDACTED]	
Initial version dated 05-Jan-2017

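### The adjusted OS model names three covariates, lets backward selection at 0.15 remove them, and still promises an HR for each; with 390 deaths there is no need to select

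*SAP*

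**What the plan says.** SAP 7.5.1.2 lists four OS sensitivity analyses under the words "The following OS sensitivity analyses will be performed". The fourth is a multivariate Cox model meant to estimate the treatment effect with three baseline covariates included: age (continuous), steroid use (yes or no) and Karnofsky status (80 or below against above 80).

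The item then sets a selection rule: "Backward selection method will be used to eliminate non-significant covariates at level 0.15".

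It closes with the output: "The hazard ratio associated with treatment and with each of the baseline covariates will be presented along with associated 95% CIs".

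Item 4 does not say that treatment is always kept, and it does not mention stratification. The SAP document history (section 10, version 3.0) supplies the second point. It explains that prior surgery was removed from the covariate list "since the model is stratified by IVRS resection which would correlate with the covariate". Resection is therefore a stratum and cannot be eliminated.

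The primary OS comparison is the stratified log-rank test (SAP 7.5.1.1). The primary HR comes from a stratified Cox model with treatment as the only covariate (protocol 8.4.2.1). Neither involves selection.

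**The concern.** The covariates are chosen in advance, but the survival data then decide which of them stay. This causes three difficulties.

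- **The rule conflicts with its own output.** A covariate that has been eliminated has no HR in the final model, yet an HR for each is promised.
- **Selection serves no purpose here.** The candidate list is short and the number of deaths is large. Nothing in the public text gives a reason for reducing the model.
- **The covariate HRs that survive are distorted.** A covariate is reported only if its estimate was large enough to pass the 0.15 threshold. Weak effects are then exaggerated, and an ordinary 95% CI makes no allowance for that filter.

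What is at stake is the clarity of a supportive analysis. If steroid use or Karnofsky status turned out imbalanced, a reader would look to item 4 for the OS effect adjusted for that factor, and might find that the factor had been removed.

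**Working it through.** **Inputs from the documents.** At least 390 deaths, target HR 0.72, two-sided alpha 0.05, 90% power, about 550 subjects randomized 1:1, control median 13.0 months, 10 months of accrual (SAP section 5). Stay level 0.15 and three covariates (SAP 7.5.1.2).

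**Assumptions.** Prognostic HRs and prevalences are not in the documents, so ranges are shown. The formulas treat one covariate at a time with a normal approximation.

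**The plan's own figure.** Schoenfeld: 4(1.960 + 1.282)²/(ln 0.72)² = 389.5, so 390 deaths. Critical HR: exp(−1.96 × 2/√390) = 0.820, and 13.0/0.820 gives a median of 15.85 months. The SAP states 390, 0.82 and 15.8, so it is reproduced.

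**Is selection needed?** 390/3 = 130 deaths per covariate, or 390/4 = 97.5 per coefficient if treatment is counted. Model size is not a constraint.

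**How often is a real factor dropped?** A two-sided 0.15 level means |z| < 1.44 leads to removal. For a binary factor with prevalence p, z is approximately normal with variance 1 and mean √(390·p(1−p))·ln HR. Example at HR 1.2 and p = 0.5: mean = 9.874 × 0.1823 = 1.80, and P(|z| < 1.44) = 35.9%.

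| Assumed HR | p = 50% | p = 30% | p = 20% |
|---|---|---|---|
| 1.15 | 52.1% | 56.6% | 62.6% |
| 1.2 | 35.9% | 41.6% | 49.8% |
| 1.3 | 12.5% | 17.5% | 26.3% |
| 1.5 | 0.5% | 1.3% | 3.9% |

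For age the mean is √390·ln(HR per SD). The drop probability is 32.9% at 1.1, 9.3% at 1.15 and 1.5% at 1.2 per SD.

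A null covariate is dropped 85% of the time. If all three were null and independent, all would go with probability 0.85³ = 61%, which leaves a model with treatment alone.

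**What happens to a retained covariate's own CI?** If the true effect is null, the CI covers only when 1.44 < |z| < 1.96, given |z| > 1.44: (0.15 − 0.05)/0.15 = 67%. For a binary factor at 30-50% prevalence:

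| True HR | Coverage if retained | Average HR if retained (geometric mean) |
|---|---|---|
| 1.0 | 67% | 1.00 |
| 1.1 | 88-89% | 1.22-1.24 |
| 1.15 | about 94% | 1.25-1.27 |
| 1.2 | about 96% | 1.27-1.29 |
| 1.3 | about 97% | 1.33-1.35 |

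Undercoverage is confined to null and weak effects.

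**What happens to the treatment HR?** This was simulated with a stratified Cox model, 550 subjects, 390 deaths, 10-month accrual and 1,500 replicates per scenario. Treatment HR was 1.0 or 0.72. Covariates ranged from all null to HRs of 1.3 (age per SD), 1.4 and 1.5, and one set was correlated.

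| Treatment HR result | All three forced in | Backward selection |
|---|---|---|
| 95% CI coverage | 94.7-95.4% | 94.5-95.5% |
| Type I error | 4.6-5.1% | 4.5-5.4% |
| Power at HR 0.72 | 88.2-90.1% | 88.6-90.3% |

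The simulation standard error of a 95% coverage figure is √(0.95 × 0.05/1500) = 0.6 points, so the columns do not differ detectably. The change in log HR caused by selection averaged at most 0.005, with a 95th percentile of at most 0.013 and a maximum of about 0.03, against an SE of about 0.10.

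**The case against.** The strongest objection is that the drop probabilities measure the wrong thing. Item 4 exists to estimate the treatment effect, and the covariates dropped most often are those whose adjustment matters least. A two-SD imbalance in a 50%-prevalence factor with 275 per arm is 2√(2 × 0.25/275) = 8.5 percentage points. At HR 1.2 this moves the treatment log HR by about 0.085 × 0.182 = 0.016. Strong factors are almost never removed. This stands in full, and it limits the point to a minor one.

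Three stronger readings are tempting, and the documents do not support them.

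- **A reader might infer that the treatment CI, the type I error or the primary result is compromised.** The primary test and HR involve no selection, item 4 carries no alpha, and the simulation shows the treatment CI keeping its coverage.
- **A reader might infer that item 4 is the only safeguard against chance imbalance outside resection.** Randomization and the primary test already control the type I error. Age, Karnofsky status and corticosteroid use are tabulated by arm (SAP 7.3.2), and subset HRs are planned for all three (SAP 7.5.1.3). Item 4 is, however, the only one of the four OS sensitivity analyses that gives an overall estimate adjusted for them.
- **A reader might infer open-ended analyst discretion.** The candidates, the method and the level are all fixed in advance. Only the resulting set depends on the data.

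It can also be said that the promised HRs are meant only for covariates that survive. That reading is possible, but the sentence does not say so, and it leaves the bias in the retained HRs.

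**Conclusion.** The point holds as a minor, cost-free improvement. Item 4 contains a selection step that 390 deaths and three covariates do not require, and that step conflicts with the item's stated output. It would often discard a real binary factor of modest strength: 52-57% of the time at HR 1.15 and 36-42% at HR 1.2. It would also leave the retained covariates' HRs exaggerated and, for null or very weak effects, their CIs too narrow.

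These sizes rest on assumed HRs and on prevalences of 30-50%. They do not describe age, which as a continuous covariate is harder to lose. The drop and coverage figures also rest on the one-covariate normal approximation. The treatment HR in item 4 changes negligibly and the primary OS conclusion not at all.

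**What to change.** In SAP 7.5.1.2 item 4, delete the backward-selection sentence. State instead that one Cox model, stratified by resection as recorded in the IRT, will contain treatment arm, age (continuous), steroid use and Karnofsky status, all forced in. Report the treatment HR and the three covariate HRs with 95% CIs beside the primary HR. If the sponsor wants to keep a selected model, label it exploratory and show it after the fixed one.

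The cost is one sentence removed and one clarified. Data, model class and sample size stay the same, and simulated power is essentially unchanged. The revised text also settles the two matters item 4 leaves unstated: that treatment is always retained and that the model is stratified.

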7.5.1.3 Consistency of Treatment Effect on OS in Subsets

To assess consistency of treatment effects in different subsets, a “forest” plot of the OS hazard ratio (and 95% CI) will be produced for the following variables, but not limited to:

- Baseline measurable lesion (yes vs. no) (source: CRF)
- Region (US/Canada vs. Europe vs. Rest of World)
- Age categorization (< 65 , $\geq 65 - < 75$, ≥ 75 , ≥ 65)
- Age categorization (< 50 , $\geq 50 - < 65$)
- Gender (Male vs. Female)
- Race (White, African American, Asian, Other)
- RPA class (III, IV, V, other)
- Smoking status (yes vs. no, unknown)
- Baseline Performance Status (Karnofsky scale) (≤ 80 , > 80)
- Baseline Pathology (Glioblastoma vs. Gliosarcoma)
- Baseline Corticosteroid use (No, Yes)

If a subgroup category has less than 10 subjects in a treatment group, then HR will not be reported for that subgroup.

7.5.1.4 Subject Follow-Up

The extent of follow-up defined as the time between randomization date and last known date alive (for subjects who are alive) or death date (for subjects who died). It will be summarized descriptively (median, min, max) in months for all randomized subjects.

The currentness of follow-up, defined as the time between last OS contact (i.e., last known date alive or death date) and data cut-off date (defined by last patient last visit date), will be summarized in months by treatment group. Subjects who died and subjects with a Last Known Date Alive on or after LPLV will have a value of '0' for currentness of follow-up. The currentness of follow-up will be categorized into the following categories: 0 days, 1-30 days, 31-60 days, 61-90 days, 91-120 days, 120-150 days, 151 or more days.

Minimum follow-up for OS, defined as the time from cutoff date to last subject's randomization date, will be summarized in months for all randomized subjects.

7.5.2 Interim Analysis

No interim analyses is planned for this study.

7.5.3 Progression Free Survival

7.5.3.1 Primary Analysis

The PFS curves for each treatment group will be estimated using the Kaplan-Meier (KM) product-limit method. Median PFS and the corresponding two-sided 95% confidence intervals using the log-log transformation will be computed.

PFS will be compared between the two randomized arms using two-sided (5% alpha level) stratified log-rank test. This comparison will only be tested if OS comparison is positive.

In addition, a stratified Cox proportional hazards regression model will be used to estimate hazard ratio between treatment groups along with the 95% CI.

PFS rates at 6, 9, 12, and 18 months will be estimated using KM estimates on the PFS curve for each treatment group. Minimum follow-up must be longer than the time point to generate the rate. The associated two-sided 95% CI will also be calculated.

The source of progression (death vs. progression) will be summarized by treatment group.

The status of subjects who are censored in the PFS KM analysis will be tabulated for each treatment group using the following categories:

- On-study (on-treatment, in follow-up)
- Off-study (lost to follow-up, withdrawn consent, never treated)
- No baseline tumor assessment
- No on-study tumor assessment and no death

- Received subsequent anti-cancer therapy

[figure not shown]
A by-subject listing will be presented including treatment arm, PFS, whether the subject was censored, and if censored, the subject’s status.

7.5.3.2 Sensitivity Analysis

Sensitivity analyses of PFS will also be performed using the following modification:

- 1) PFS accounting for assessment after subsequent therapy. It will be defined similar to the primary definition except that events (progression or death) and tumor assessments that occurred after subsequent anticancer therapy or diagnostic surgical resection will be taken into account (see censoring scheme 1 for sensitivity analysis in Figure 7.5.3.2-1).

Figure 7.5.3.2-1: Graphic Display of PFS Accounting for Assessment after Subsequent Therapy

- 2) PFS not considering clinical progression as event: It will be defined same as the primary definition except not considering clinical progression as progression event.
- 3) PFS accounting for assessment after subsequent therapy and not counting clinical progression as event: It will be defined same as sensitivity analysis #1 defined above except not considering clinical progression as progression event.

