After cessation of study treatment for any reason, all randomized subjects will enter a **follow up** phase. In the short-term, visits are defined for reporting of treatment-related AEs. All subjects in whom disease progression had not been detected at the time study treatment is stopped will be followed closely for progression with contrast enhanced MRI every 8 weeks (\pm 7 days) until progression. After progression, subjects **MUST** be followed for survival (primary endpoint); subsequent treatments will be reported. For details on the follow-up phase, see [section 3.1.3](#).

Baseline and all subsequent scans will be submitted to a blinded independent radiology review committee (BIRC) for archiving, once the subject is randomized and throughout the study period.

A Data Monitoring Committee (DMC) will meet regularly during the study to ensure that subject safety is carefully monitored, see [Section 7](#).

The study design schematic is presented in [Figure 3.1-1](#).

Figure 3.1-1: Study Design Schematic

[figure not shown]

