4.5.1.6 Continuing Nivolumab with Suspected Progression

Accumulating evidence indicates that a minority of subjects treated with immunotherapy may derive clinical benefit despite initial evidence of disease progression, eg, due to inflammatory reaction simulating progression (“tumor flare” or pseudoprogression). Subjects on the RT + nivolumab arm may, at investigator discretion, continue nivolumab in the setting of suspected progression until progression is confirmed. [Note: this is not the same as confirmation of progression occurring within 12 weeks after RT, which applies to both treatment arms.] Communication with the BMS Medical Monitor is strongly encouraged. If the investigator believes that the subject continues to derive clinical benefit by continuing treatment, the subject should continue assessments according to [Table 5.1-2](#).

Subjects may continue nivolumab beyond initial (suspected) progression only if they meet the following criteria:

- Subject is tolerating nivolumab

- Treatment will not delay intervention to prevent imminent complications, eg surgery for relief of symptomatic intracranial mass effect
- Investigator-assessed overall clinical benefit

Radiographic assessment should be repeated after suspected progression as clinically required in order to determine whether there has been a decrease in the tumor size or continued progression. If possible, perfusion images should also be obtained. All MRI scans should be submitted to the imaging vendor as soon as possible.

Re-operation should be considered, if lesion is surgically accessible, to differentiate immune-treatment effects from progression. The BMS Medical Monitor should be consulted. Potential for clinical benefit should be balanced by clinical judgment as to whether the subject is clinically deteriorating and unlikely to receive benefit from continued treatment with nivolumab. Nivolumab treatment should be discontinued permanently upon confirmation of RANO-assessed progression but prolonged observation (eg, 3 months) may be required, as suggested in Okada et al.⁴⁰

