Targeted Physical Examination, Vital Signs	Q2 wks	Day 1 of each cycle	Q2 wks x 8 doses, then Q4 wks	Weight, BP, HR, RR, temperature, and Karnofsky Performance Status
Adverse Events Assessment	Continuously			Record at each visit
Review of Concomitant Medications	X	X	X	Record at each visit, including steroid dose
Radiation Therapy	See Note		See Note	Total dose 60 Gy over 6-7 weeks, see Section 3.1.2.2
CBC with Differential	Weekly	Day1&22 of each cycle	Within 3 days prior to each dose	Weekly if delayed and as clinically indicated
Chemistry panel	Q4 wks	Day 1 each cycle	Within 3 days prior to each dose	Chemistry panel: AST, ALT, ALP, T.Bili, albumin, BUN or serum urea, creatinine, Ca, Na, K, Cl, LDH, Glucose Additional tests, as clinically indicated, will also be submitted
Thyroid Function Test		X	X	TSH every 8 weeks, T3 and T4 (Free or Total, if TSH abnormal) and as clinically indicated
Pregnancy Test [WOCBP only]	Every 4 weeks			Serum or urine pregnancy test every 4 weeks (± 3 days; minimum sensitivity 25 IU/L or equivalent units of HCG).
				
Tumor Assessment	X (See Note)			Contrast-enhanced MRI 4 weeks (± 7 days) after completing RT, then every 8 weeks (± 7 days) ^a until progression. See Section 5.4.1
				

Table 5.1-2: On-Treatment Assessments (CA209498)

Procedure	RT + TMZ	TMZ Maintenance	RT + Nivolumab	Notes: Windows refer to calendar days. Procedures must be done within 72h prior to dosing unless otherwise specified.
[REDACTED]		[REDACTED]		[REDACTED]
[REDACTED]		[REDACTED]		[REDACTED]
[REDACTED]		[REDACTED]		[REDACTED]
Health Care Resource Utilization		X (See Note)		Obtained prior to dosing Day 1 Week 1 and then with each MRI, (± 7 days) see Section 5.8.4
[REDACTED]		[REDACTED]		[REDACTED]
Dispense Nivolumab			X (see note)	Day 1 within 7 days of randomization, then every 2 weeks for 8 doses, then every 4 weeks
Dispense Temozolomide	D1, D15, D29 & D43 (if needed)	D1 each cycle		Temozolomide taken daily during RT then 4 week break, then daily x 5 in 28-day cycles x 6 cycles, see Section 4.5.2
Tumor Sample at time of progression or suspected progression	At time of PD or suspected PD			If biopsy or surgical resection is performed at progression or suspected progression, a tumor sample (block or slides) should be submitted for central neuropathologic review
Assess Temozolomide Compliance	X	X		Review medication diary

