^a Per RANO, assessment of disease progression during study requires that MRI scan be performed >12 weeks after RT; it is, therefore, recommended that second on-treatment scan be performed at least 84 days after completion of RT.

Table 5.1-3: Treatment Follow-up and Survival Follow-Up (CA209-498)

Procedure	Treatment Follow-up ^a	Survival Follow-up ^b	Notes
TIMING	35 and 115 days (±7 Days) after last dose	Q 3 Months (± 14 Days)	
Targeted Physical Examination	X		Weight, BP, HR, RR, temperature and Karnofsky Performance Status
Adverse Events Assessment	X	X	Beyond 100 days from the last dose of study treatment subjects will be followed for ongoing drug-related adverse events until resolved, return to baseline or deemed irreversible or until lost to follow-up or withdrawal of study consent
Laboratory Tests	X		CBC w/differential, LFTs, BUN, creatinine and TSH at 35 days, repeat labs at 115 day visit if study drug-related toxicity persists.
Pregnancy Test [WOCBP only]	X		Serum or urine pregnancy test (minimum sensitivity 25 IU/L or equivalent units of HCG).
Review of Concomitant Medications	X		
Tumor Assessment	X Q8 weeks (± 7 days) until PD		Required for subjects who did not progress on study treatment, eg, discontinued for AEs.
NANO scale	X	X	Completed by study physician with each MRI (± 7 days)
Cogstate		X	Cogstate Assessments should occur at Months 6, 12, 18, and 24 (± 15 days) and then continue every 12 months (± 15 days) as long as MRIs are performed. See Section 5.7.1 .
Biomarker Sample	X		Serum and whole blood at time of progression; See Section 5.6 .
Tumor Sample at time of progression	X	X	If biopsy or surgical resection is performed at the time of progression or suspected progression, a tumor biopsy sample (block or slides) should be submitted for central neuropathologic review.
EORTC QLQ-C30 and BN20	X		
EQ-5D	X	X	May be obtained through telephone call or clinic visit
Survival Status		X	Every 3 months (± 14 days) (clinic visit or telephone contact), during Survival phase, include documentation of subsequent chemotherapy.

- ^a Subjects must be followed for at least 100 days after last dose of study treatment. Follow-up visit #1 (FU1) occurs approximately 35 days (± 7 days) after the last dose or coinciding with the date of discontinuation (± 7 days) if date of discontinuation is greater than 30 days after last dose. Follow-up visit #2 (FU2) occurs approximately 115 days (± 7 days) after the last dose

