5.4.1 Suspected Progression

In order to distinguish potential treatment effects (or “pseudoprogession”) from progressive disease and thus to minimize premature discontinuation of nivolumab or temozolomide, subjects who initially meet radiologic criteria for disease progression, but are tolerating study drug, may continue receiving study drug until confirmation of progression with an MRI performed approximately 8 weeks later. If possible, MRI perfusion images should also be obtained. If a determination cannot be made after an 8 week interval, then treatment may continue until either progression is confirmed or regression is observed, consistent with either pseudoprogession or

immune-treatment effect. Consultation with the BMS Medical Monitor is recommended but not required.

Confirmation of progression is mandatory if recurrence occurs within 12 weeks of completion of RT. Suspected disease progression within 12 weeks after the end of RT must be confirmed by subsequent MRI performed within 8 weeks after the initial radiological assessment of progression. Prior to 12 weeks after RT, progression can only be defined using diagnostic imaging if there is new enhancement outside of the radiation field (beyond the high-dose region or 80% isodose line) or if there is unequivocal evidence of viable tumor on histopathologic sampling.³⁹ Note: in the absence of radiographic or histologic confirmation of progression, clinical decline alone is not sufficient for definition of progressive disease.

If the follow-up assessment confirms that progression has occurred, the date of progression will be the date at which progression was first determined. If the follow-up assessment does not confirm progression, then the original time point response will be assessed as SD.

[REDACTED]

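### Do the PFS sensitivity analyses that drop clinical progression show that the tested PFS counts events Protocol 5.4.1 does not accept?

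*SAP*

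**What the plan says.** **Primary PFS.** SAP 4.2.1 and Protocol 8.3.2 count the first documented tumor progression or death, determined from the investigator's reported response under RANO. Neither mentions clinical progression. SAP 7.5.3.1 tests PFS with a stratified log-rank test at two-sided 5%, only if OS is positive. The study is open-label (SAP 2.3).

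**Sensitivity analyses (SAP 7.5.3.2).** Analysis 1 also uses events and scans after subsequent therapy or resection. Analysis 2 is "PFS not considering clinical progression as event: It will be defined same as the primary definition except not considering clinical progression as progression event". Analysis 3 makes the same exception to analysis 1.

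**Calling progression (Protocol 5.4.1).** "Confirmation of progression is mandatory if recurrence occurs within 12 weeks of completion of RT". "Prior to 12 weeks after RT, progression can only be defined using diagnostic imaging if there is new enhancement outside of the radiation field" or on unequivocal histology. The paragraph ends with the note that "in the absence of radiographic or histologic confirmation of progression, clinical decline alone is not sufficient for definition of progressive disease". The next paragraph dates a confirmed progression to when it was first determined and treats an unconfirmed one as stable disease. Protocol 4.5.1.6 separates this rule from continuing nivolumab at suspected progression: "this is not the same as confirmation of progression occurring within 12 weeks after RT, which applies to both treatment arms".

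**Scans (Protocol Table 5.1-2).** "Contrast-enhanced MRI 4 weeks (± 7 days) after completing RT, then every 8 weeks"; footnote a adds that it is "recommended that second on-treatment scan be performed at least 84 days after completion of RT".

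**The concern.** Had the primary definition never counted clinical progression, analysis 2 would duplicate the primary and analysis 3 would duplicate analysis 1. Including them suggests that the author expected such events in the primary. The visible SAP text does not define the term, carries no exception for the 12 weeks after RT and does not repeat the confirmation rule.

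PFS is the only secondary endpoint with a formal test, and an unblinded investigator assesses it. In the weeks after RT, pseudoprogression is the main difficulty, and only one scheduled on-study scan precedes the 12-week point. If purely clinical calls counted there, the tested endpoint would include events that the protocol does not recognise. The planned source-of-event table, which separates only death from progression, would not show them.

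**Working it through.** **1. The plan's own figure.** Neither document sizes PFS. The only design figure is for OS: 4 × (1.960 + 1.282)² / (ln 0.72)² = 389.5, so 390 deaths; the critical hazard ratio is exp(−1.960 × 2/√390) = 0.82. Both match Protocol 8.1 and SAP 5. The point does not depend on them.

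**2. Do the passages conflict?** They do only if the SAP's clinical progression means an unconfirmed clinical call within the period that the protocol note governs. Three readings give analyses 2 and 3 content:

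| Reading of clinical progression | Analyses 2 and 3 have content? | Conflict with Protocol 5.4.1? |
|---|---|---|
| Unconfirmed call within 12 weeks after RT | Yes | Yes |
| Clinically based call after that period | Yes | Not shown; the note's reach is open |
| Clinical call later confirmed by MRI or histology | Yes; removing it can drop or re-date the event | No |

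No visible SAP sentence selects the first reading. Because the SAP takes PFS from the investigator's RANO-based response, and 5.4.1 limits what the investigator may report, the SAP can be read as inheriting the limit. Figure 4.2.1-1 and the protocol's RANO sections (cited as 5.4.2 and 5.4.3) are not in the public text, so a definition may sit there.

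**3. Timing.** RT starts 0–1 week after randomization (Protocol 3.1.2.1) and lasts 6–7 weeks (3.1.2.2), so it ends at weeks 6–8. The 12-week point falls at weeks 18–20, or 4.1–4.6 months. The first scan falls 4 weeks after RT (weeks 10–12), so 4/12 = 33% of the post-RT period precedes it.

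**4. How many subjects could be involved?** Median PFS m is assumed, with exponential times. The expected number of PFS events between weeks a and b is 550 × (2^(−a/m) − 2^(−b/m)), with weeks converted to months by 7/30.4375.

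| Assumed median | Randomization to weeks 18–20 | 12 weeks after RT only |
|---|---|---|
| 4 months | 282–302 | 152–165 |
| 6 months | 209–227 | 121–128 |
| 8 months | 166–181 | 100–104 |

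Counting from randomization gives 1.6–2.0 times as many events and includes the RT period (about 62–150 events under this model), when no on-study scan is scheduled. If 5% to 20% of the post-RT events were clinical-only (also assumed), that is 0.05 × 100 = 5 to 0.20 × 165 = 33 subjects. Each would be a departure from 5.4.1, and nothing in the documents indicates how common such departures are. Equal shares in both arms with no true effect leave the hazard ratio at 1.00.

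**5. What would removing such calls cost?** Under SAP 4.2.1, a subject who starts new therapy with no reported progression is censored at the last prior scan, and one with no on-study scan at randomization. A simulation illustrates the effect: median 6 months, uniform accrual over 10 months, cutoff at month 33, calls spread over weeks 0–19 from randomization (the longer period), and every removed call followed by a therapy switch.

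| Share clinical-only | Events counting the calls | Events with the calls removed |
|---|---|---|
| 5% | 528 | 516 |
| 10% | 528 | 505 |
| 20% | 530 | 478 |

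The losses are 12, 23 and 52 events (2%, 4% and 10%). They are also informative, because they come from subjects thought to be deteriorating.

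**The case for a change.** The strongest opposing argument is that the exception presupposes clinical events in the primary, that 4.2.1 lists censoring rules in detail yet is silent here, and that one sentence would settle the matter before analysis. If the SAP inherits 5.4.1, the sentence costs nothing; if not, it repairs the tested endpoint. Analyses 2 and 3 would reveal dependence on clinical calls but do not decide which definition the test uses.

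Part of this stands. The term is undefined in the visible text, and a definition would be tidier. The rest does not require a change. Sites work from the protocol, so 5.4.1 binds the report that feeds PFS whether or not the SAP repeats it. A subject whose call does not qualify remains under imaging: "All subjects in whom disease progression had not been detected at the time study treatment is stopped will be followed closely for progression". Scans might in practice stop once clinical progression is recorded, and that practical risk would remain after an edit to the SAP. Removing reported clinical calls from the tested endpoint is also not plainly better, given the informative censoring shown above; statisticians differ on that choice. The plan already gives both versions, and analysis 3 also uses what happens after a therapy switch.

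**Conclusion.** No change follows. There is a small gap, an undefined term in SAP 7.5.3.2, which an analyst can fill by applying Protocol 5.4.1 to the investigator-reported RANO response. A sponsor that follows 5.4.1 as written obtains a sound primary PFS, and restating the rule would then alter no result. Whether clinical calls outside the reach of 5.4.1 should count is a trade-off between a less objective event and informative censoring, and the sensitivity analyses already show both sides.

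The size and direction of any effect on the PFS hazard ratio cannot be determined from the documents. The range of 5 to 33 of 550 subjects rests on assumed medians of 4 to 8 months, exponential times, RT on schedule, and an assumed clinical-only share of 5% to 20%. The conclusion also allows for Figure 4.2.1-1 and the RANO sections being unseen. If either stated that unconfirmed clinical decline within 12 weeks of RT is a primary PFS event, the conflict would be real and the passages would need to be reconciled. OS is unaffected in every case.
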